6.2.5.2 Baseline Disease Characteristics

Migraine History

Refer to the Core SAP for the table of migraine history.

History of CV Events, Conditions, Procedures, and Other Risk Factors

Results are based on the History of CV Events, Conditions, Procedures, and Other Risk Factors CRF.

The frequency table of history of CV events, conditions, procedures, and other risk factors displays the number and percentage of subjects in the following categories and subcategories based on “yes” responses to CRF questions:

- History of CV disease (event, condition, or procedure) or risk factor. Defined as any of the 4 categories listed below.
- (1) History of CV event. Defined as any of the following:
 - Cardiac arrest

- Cerebrovascular accident
- Myocardial infarction
- Transient ischemic attack
- (2) History of CV condition. Defined as any of the following:
 - Angina pectoris (myocardial ischemia)
 - Cardiac conduction disorder
 - Coronary artery vasospasm (Prinzmetal's angina)
 - Ischemic coronary artery disease
 - Ischemic bowel disease
 - Peripheral artery disease (including claudication)
- (3) History of CV procedure. Defined as any of the following:
 - Angioplasty (with or without stent placement)
 - Carotid endarterectomy
 - Coronary artery bypass grafting
- (4) Other CV disease or risk factor. Defined as any of the following:
 - Other significant underlying CV disease
 - Uncontrolled hypertension
 - Known hypersensitivity to triptan
 - Treatment for hypertension
 - Diabetes
 - Current smoker
 - Treatment with a statin
 - Family history of coronary artery disease.

Results are displayed for all categories and subcategories, even those with 0 counts.

Triptan-Unsuitable Criteria

Results are based on the Triptan-Unsuitable Criteria CRF.

The frequency table of triptan-unsuitable criteria displays the number and percentage of subjects in the following categories:

- History of documented failure to ≥ 2 triptan medications or documented contraindication to the use of triptans. These 2 categories are defined below. The number of failure reasons are the following mutually exclusive subcategories:

- All 3 reasons: lack of efficacy, prior intolerance, and documented contraindication to the use of triptans
- Only 2 reasons
- Only 1 reason.
- History of documented failure to ≥ 2 triptan medications
 - History of documented failure to a triptan is defined as a triptan meeting all the following criteria:
 - Nonstudy medication type of previous; refer to the Core SAP for the definition.
 - “Lack of efficacy” or “prior intolerance” as a reason for failure.
 - Triptan medications are identified from 7 distinct triptan names, i.e., almotriptan, eletriptan, frovatriptan, naratriptan, rizatriptan, sumatriptan, or zolmitriptan.
 - The following reasons for failure are subcategories:
 - Lack of efficacy. Defined as ≥ 1 reason due to lack of efficacy.
 - Prior intolerance. Defined as ≥ 1 reason due to prior intolerance.
 - Lack of efficacy and prior intolerance. Defined as ≥ 1 reason due to lack of efficacy and ≥ 1 reason due to prior intolerance.
- Documented contraindication to the use of triptans. Defined as “yes” response to (1) the question “Does the subject have documented contraindication to the use of triptans?” or (2) any of the 4 CRF questions about reasons for contraindication. Reasons are the following subcategories:
 - Specified CV event, condition, or procedure *
 - Documented hypersensitivity to triptans *
 - Uncontrolled hypertension *
 - Other aspects *
 - Not reported.

Categories marked with “*” are based on “yes” responses to CRF questions.

The listing of triptan-unsuitable criteria is provided for the enrolled analysis set. The listing displays the following parameters in columns: history of documented failure to ≥ 2 triptan medications status (“Y” or missing), as defined above; documented contraindication to the use of triptans (“Y” or missing), as defined above; response (yes, no) to each contraindication reason category marked with “*”; and triptan medication names and reason(s) for failure (lack of efficacy, prior intolerance). Additional triptan medication parameters (e.g., start and end dates) are presented in the by-subject listing of nonstudy medications (see Section 6.2.6.3).

Migraine Characteristics at the Time of DB Study Drug Dosing

Migraine characteristics at the time of DB study drug dosing include the following parameters from the eDiary:

- Migraine headache pain intensity (none, mild, moderate, severe)
- MBS before DB study drug dosing (nausea, phonophobia, photophobia)
- Nausea status (present, absent)
- Nausea intensity (none, mild, moderate, severe)
- Phonophobia status (present, absent)
- Phonophobia intensity (none, mild, moderate, severe)
- Photophobia status (present, absent)
- Photophobia intensity (none, mild, moderate, severe)
- Functional disability level (normal, mildly impaired, severely impaired, requires bedrest)
- Aura status preceding or accompanying headache (yes, no).

An intensity of none for a symptom (nausea, photophobia, or phonophobia) is defined as a symptom status of absent.

See Section 7.4.2 for additional details.

6.2.5.3 Medical History

The frequency table of medical history is provided by system organ class (SOC) and preferred term (PT), and is displayed in descending order of overall frequency within SOC and PT.

The frequency table of medical history of hypertension by SOC and PT is also provided.

6.2.5.4 Nonstudy Prior Medications

Frequency tables of the following nonstudy medications are provided by therapeutic class and preferred name:

- Previous triptan medications for the DBT efficacy analysis set
- Previous triptan medications for the DBT efficacy analysis set with documented contraindication to the use of triptans (see Section 6.2.5.2)
- Previous triptan medications failed due to lack of efficacy or prior intolerance for the DBT efficacy analysis set with history of documented failure to ≥ 2 triptan medications (see Section 6.2.5.2)
- Previous triptan medications failed due to lack of efficacy for the DBT efficacy analysis set with history of documented failure to ≥ 2 triptan medications with ≥ 1 reason due to lack of efficacy (see Section 6.2.5.2)

- Current medications for the DBT safety analysis set: all; acute migraine; prophylactic migraine.

Medications are displayed in descending order of overall frequency within therapeutic class and preferred name. See Section 6.2.6.3 for the definition of acute migraine and prophylactic migraine medications. Refer to the Core SAP for the definitions of previous, current, and triptan medications.

6.2.6 Exposure

See Section 7.1 for derived dates.

6.2.6.1 Study Therapy

The by-subject listing of study drug dosing and accountability is produced for the safety analysis set and displays OL rimegepant start and end date/times, time in the OLE Phase (weeks), cumulative OL rimegepant exposure (tablets), average OL rimegepant exposure (tablets per month), kit dispensed date, kit returned date, study drug date/time (see Section 7.1), eDiary source (reported prospective, reported retrospective, manual data correction form [DCF]; see Section 7.4.1), wallet ID, and study drug type (DB rimegepant, DB placebo, OL rimegepant). The listing is sorted by site-subject ID, kit dispensed date, study drug date/time, and eDiary source. Invalid wallet IDs are identified.

Wallet IDs are collected on the Drug Accountability CRF with yes/no questions about wallet dispensed or returned status, and corresponding wallet dispensed and returned dates. Wallet IDs are compared to the study drug wallet list file to determine wallet type (DB rimegepant, DB placebo, or OL rimegepant). Valid wallet IDs are those in the study drug wallet list file.

OL Rimegepant Exposure

The table of OL rimegepant exposure is provided by treatment group/OL rimegepant and overall for the OL rimegepant safety analysis set, and summarizes the following parameters descriptively as continuous or categorical variables:

- Time on OL rimegepant (weeks), derived as $(\text{OL rimegepant end date} - \text{OL rimegepant start date} + 1)/7$
- Time on OL rimegepant (weeks) categories: <2 , ≥ 2 to <4 , ≥ 4 to <6 , ≥ 6 to <8 , ≥ 8 to <10 , ≥ 10 to <12 , ≥ 12 to <14 , and ≥ 14
- Time in the OLE Phase (weeks), derived as $(\text{OLE Phase end date} - \text{OLE Phase start date} + 1)/7$
- Time in the OLE Phase (weeks) categories: <2 , ≥ 2 to <4 , ≥ 4 to <6 , ≥ 6 to <8 , ≥ 8 to <10 , ≥ 10 to <12 , ≥ 12 to <14 , and ≥ 14
- Cumulative OL rimegepant exposure (tablets), derived by summing number of tablets across records with complete OL rimegepant study drug date

- Average rimegepant exposure (tablets per month), derived as (1) cumulative OL rimegepant exposure (tablets) if time in the OLE Phase <2 weeks, or (2) $4 \times$ cumulative OL rimegepant exposure / {time in the OLE Phase}, if time in the OLE Phase ≥ 2 weeks
- Total OL rimegepant exposure (tablets) summed across all subjects, derived by summing cumulative OL rimegepant exposure across all subjects
- Total OL rimegepant exposure (patient-years), derived by summing (OL rimegepant end date – OL rimegepant start date + 1)/365.25 across all subjects.

See Section 7.4.1 for tablet counts.

Tables of OL rimegepant exposure are also provided by subgroup level and overall for all high-level safety subgroups of interest described in Section 4.3.2.

6.2.6.2 *Measurements of Treatment Compliance*

The by-subject listing of treatment compliance is provided for the safety analysis set, and displays results for DB and OL rimegepant treatment compliance parameters in separate columns as flags (“Y” or missing).

DB Treatment Compliance

The frequency table of DB study drug treatment compliance is provided by treatment group for the DBT safety analysis set, and displays the following categories:

- DB study drug taken but not randomized. Defined as nonmissing DB study drug date and missing RTSM randomization date.
- DB study drug taken without having a qualifying migraine attack. Defined as nonmissing DB study drug date and no qualifying migraine attack at the time of DB study drug dosing (see Section 9.3.1).
- DB study drug actually received different from randomized treatment assignment (i.e., as-treated treatment group not equal to as-randomized treatment group). Defined as either of the following using the Drug Accountability CRF:
 - Randomized to rimegepant but the first wallet dispensed is DB placebo
 - Randomized to placebo but the first wallet dispensed is DB rimegepant.

Results for all categories are displayed, even those with 0 counts.

OL Rimegepant Treatment Compliance

The frequency table of treatment compliance is provided by treatment group for the OL rimegepant safety analysis set, and displays the following categories:

- >1 OL rimegepant tablet taken on any 1 day
- OL rimegepant taken before OLE Phase eligibility contact. Defined as OL rimegepant start date before the contact date from the OLE Phase Eligibility CRF.

- OL rimegepant taken without having a qualifying migraine attack. Defined as nonmissing OL rimegepant date and no qualifying migraine attack at the time of OL rimegepant dosing (see Section 9.3.1)
- Time on OL rimegepant ≥ 14 weeks (see Section 6.2.6.1)
- OL rimegepant taken but DB study drug never taken. Defined as missing DB study drug date/time.

Results for all categories are displayed, even those with 0 counts.

6.2.6.3 Nonstudy Concomitant Medications

Frequency tables of the following nonstudy medications are provided by treatment group:

- DBT concomitant for the DBT safety analysis set: all; prophylactic migraine
- DBT rescue medications for the DBT efficacy analysis set.

Medications are displayed in descending order of rimegepant frequency within therapeutic class and preferred name.

The frequency table of nonstudy post-DBT pre-OL rimegepant medications is provided by treatment group and overall for the interim safety analysis set. Medications are displayed in descending order of overall frequency within therapeutic class and preferred name.

Frequency tables of the following nonstudy medications are provided by treatment group/OL rimegepant and overall:

- OL rimegepant concomitant for the OL rimegepant safety analysis set: all; acute migraine; prophylactic migraine
- OLE rescue medications for the OLE migraine analysis set.

Medications are displayed in descending order of overall frequency within therapeutic class and preferred name.

Prophylactic migraine medications are displayed by preferred name without therapeutic class.

The by-subject listing of nonstudy medications is provided by therapeutic class and preferred name for the enrolled analysis set. Acute migraine, prophylactic migraine, and rescue medications are identified. For rescue medications, the medication date/time is displayed instead of the medication start and end dates. The listing also displays abbreviated medication types comma-concatenated in the following order: previous ("P"); current ("C"); DBT concomitant ("D"); post-DBT pre-OL rimegepant ("T"); OL rimegepant concomitant ("O"); follow-up ("F"). A medication may be classified into multiple medication types. See Section 7.6 for the definition of the last 4 medication types.

Refer to the Core SAP for the following: counting rules in nonstudy medication frequency tables; non-study medication start and end date imputation; and definition of previous and current medication types.

Note that medications on the Rescue Medication CRF are collected with both medication date and time (where time may be missing), but not start and end dates. Imputed start and end dates for Rescue Medication CRF data are used only to derive nonstudy medication type.

Nonstudy Medications

Nonstudy medications are identified from the (1) Triptan-Unsuitable Criteria CRF, (2) Concomitant Medications CRF, or (3) Rescue Medications CRF. The Concomitant Medications CRF collects indications, and links medical history and AE terms respectively to the Medical History and AE CRFs.

Migraine Standard of Care Medications

Acute migraine-specific medications are defined as nonstudy medications with preferred name containing triptan, ergotamine, lasmiditan, or ubrogepant.

Acute migraine medications are defined as any of the following nonstudy medications:

- Acute migraine-specific medication
- Those with an indication of “acute migraine medication” from the Concomitant Medications CRF
- Those from the Rescue Medications CRF.

Prophylactic migraine medications are defined as nonstudy medications with an indication of “prophylactic migraine medication” from the Concomitant Medications CRF.

Migraine standard of care medications are defined as acute migraine or prophylactic migraine medications.

DBT Rescue Medications

DBT rescue medications are defined as DBT concomitant medications from the Rescue Medications CRF that meet any of the following criteria:

- $DB \text{ study drug date/time} < \text{medication date/time} < DB \text{ study drug date/time} + 49 \text{ hours} + 1 \text{ minute}$ (upper bound of the 48-hour postdose analysis window; see Table 7), if {DB study drug date and time are both nonmissing} and {medication date is complete and time is nonmissing}
- $DB \text{ study drug date} \leq \text{medication date} \leq DB \text{ study drug date} + 2 \text{ days}$, if {DB study drug date is nonmissing but time is missing} or {medication date is complete but time is missing}.

Thus, DBT rescue medications are a subset of DBT concomitant medications.

OLE Rescue Medications

OLE rescue medications are defined as OL rimegepant concomitant medications from the Rescue Medications CRF that meet any of the following criteria:

- OL rimegepant date/time < medication date/time < OL rimegepant date/time + 25 hours + 1 minute (upper bound of the 24-hour postdose analysis window; see Table 7), if {OL rimegepant date and time are both nonmissing} and {medication date is complete and time is nonmissing}
- OL rimegepant date ≤ medication date ≤ OL rimegepant date + 1 day, if {OL rimegepant date is nonmissing but time is missing} or {medication date is complete but time is missing}.

Thus, OLE rescue medications are a subset of OL rimegepant concomitant medications.

Note that subjects may have multiple OL rimegepant date/times. Each medication date/time is compared to each distinct OL rimegepant date/time to determine whether it is OLE rescue medication.

Acute Headache Medications

Acute headache medications are defined as any of the following nonstudy medications:

- Acute migraine medication (which includes rescue medication)
- Those with medical history term, primary AE term, additional AE term, or other specify term (1) containing “headache” or “migraine” and (2) not containing “prevent” or “prophyl” from the Concomitant Medications CRF.

Thus, acute headache medications include both rescue medications and nonrescue acute headache medications.

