9.2.1 Medication Day During the OLE Phase

9.2.1.1 Acute Migraine Medication Day During the OLE Phase

Acute migraine (rescue or non-rescue) medication days are identified from nonstudy medication CRF data and eDiary data.

Nonstudy acute headache medications taken during the OLE Phase and eDiary measurement dates during the OLE Phase are selected (see Sections 6.2.6.3 and 7.1).

Let X denote a date in the OLE Phase interval defined in Section 9.2. Then X is classified as an acute migraine medication day during the OLE Phase if any of the following criteria is met:

- X is an acute migraine-specific medication day (see Section 9.2.1.2)
- X is a migraine day (see Section 9.2.2) on which any of the following also occur:
 - Imputed medication start date $\leq X \leq$ imputed medication end date, if any given select nonstudy acute headache medication has medication frequency of QD, BID, TID, QID, QAM, or QHS
 - X is equal to the imputed start date or imputed end date, if any given select nonstudy acute headache medication does not have medication frequency of QD, BID, TID, QID, QAM, or QHS
 - X is an eDiary measurement date with “yes” response to the question about other medication taken to treat headache or aura from the eDiary Migraine question category (see Section 7.4).

All select nonstudy medication records and eDiary measurement dates are compared to X to determine whether X is an acute migraine medication day.

Acute migraine medication days are a subset of migraine days (see Section 9.2.2).

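### SAP 6.2.6.3 does not keep prophylactic drugs out of the acute headache medication class, so a daily preventive linked to a bare 'Migraine' or 'headache' term would inflate acute medication days (exploratory objective 12)

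*SAP*

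**What the plan says.** SAP 6.2.6.3 gives acute headache medications two limbs. The first is any acute migraine medication. The second covers "Those with medical history term, primary AE term, additional AE term, or other specify term (1) containing" 'headache' or 'migraine', subject to the condition "2) not containing “prevent” or “prophyl” from the Concomitant Medications CRF". The same section explains where those terms come from: "The Concomitant Medications CRF collects indications, and links medical history and AE terms respectively to the Medical History and AE CRFs". Preventives are recognised by a different field: "Prophylactic migraine medications are defined as nonstudy medications with an indication of “prophylactic migraine medication” from the Concomitant Medications CRF".

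SAP 9.2.1.1 then draws on the whole class: "Nonstudy acute headache medications taken during the OLE Phase and eDiary measurement dates during the OLE Phase are selected". A date counts if it is an acute migraine-specific medication day, which under SAP 9.2.1.2 includes every open-label (OL) rimegepant date. It also counts if "X is a migraine day (see Section 9.2.2) on which any of the following also occur". The first such occurrence is that the date lies between a medication's imputed start and end, "if any given select nonstudy acute headache medication has medication frequency of QD, BID, TID, QID, QAM, or QHS".

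For exploratory objective 12, SAP Table 4 makes nonrescue acute headache medication part of the endpoint and handles prophylactic use by a treatment policy strategy. Protocol 5.5.1 and Appendix 2 allow preventives throughout the study if they are taken regularly and the dose does not change.

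**The concern.** The only guard against preventives in the second limb is a string match on the linked term. It catches free text such as 'migraine prophylaxis'. A medical history entry, however, names a condition, and one reading simply 'Migraine' passes both conditions. The recorded indication is not consulted, so a drug can be prophylactic by indication and acute by linked term, and the SAP does not say which prevails.

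A stable preventive taken once or twice daily normally spans the whole OLE Phase. Once such a drug is in the acute class, the date-range rule marks all migraine days in that span, whether or not an acute drug was taken. Objective 12 is meant to describe acute drug use. It would then partly describe preventive use, always in the direction of more acute treatment and always in subjects on preventives.

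**Working it through.** The plan gives no figure to reproduce here, so the check applies the rules literally and then sizes the result under stated assumptions.

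**Step 1. The rules on a constructed subject.** Take a 28-day month with migraine on days 2, 5, 8, 11, 15, 18, 22 and 26 (8 days), OL rimegepant on days 2, 8, 15 and 22, and no other acute drug. Without a preventive the count is 4. Adding one preventive gives:

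| Preventive record | In acute class? | Days counted |
|---|---|---|
| QD, linked to 'Migraine', prophylactic indication | yes | 8 of 8 |
| QD, linked to 'Migraine', other indication | yes | 8 of 8 |
| QD, other-specify term 'migraine prophylaxis' | no | 4 of 8 |
| QD, prophylactic indication, no linked term | no | 4 of 8 |
| Weekly, linked to 'Migraine' | yes | 4 of 8 |
| QD, linked to 'Migraine', ended day 10 | yes | 5 of 8 (day 5 added) |

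The inflation needs three things together: a linked bare term, one of the six listed frequencies, and migraine days inside the medication dates. Excluding drugs with a prophylactic indication brings the first row back to 4 of 8 but leaves the second at 8 of 8.

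**Step 2. Size.** Let m be migraine days per month, c those already counted through OL rimegepant or another acute drug, and s the share of subjects affected.

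- Gain per affected subject = m − c
- Rise in group mean = s × (m − c)

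The documents give m only at entry (4 to 14 per month, Protocol 5.2); c and s are not given. Assume m = 8 and c = 4 to 6. The gain is 8 − 6 = 2 to 8 − 4 = 4 days.

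| s | c = 6 | c = 4 |
|---|---|---|
| 10% | 0.10 × 2 = 0.2 | 0.10 × 4 = 0.4 |
| 25% | 0.25 × 2 = 0.5 | 0.25 × 4 = 1.0 |
| 40% | 0.40 × 2 = 0.8 | 0.40 × 4 = 1.6 |

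Over a wider grid (m from 4 to 14, 50% to 90% of migraine days already counted), an affected subject gains between 4 × 0.1 = 0.4 and 14 × 0.5 = 7.0 days. With 5% to 20% affected, the mean rises by 0.05 × 0.4 = 0.02 to 0.20 × 7.0 = 1.4 days per month.

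**Step 3. Reach.** Migraine days (SAP 9.2.2) and acute migraine-specific medication days (9.2.1.2) do not use the acute headache class. Rescue medication comes from its own CRF. For the primary and key secondary endpoints, nonrescue acute headache medication is handled by treatment policy. Only objective 12 moves.

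**The case against.** The strongest reply is that the problem may never occur. The CRF has a dedicated prophylactic indication, and the terms searched may belong to other indication branches, so that a drug entered as prophylactic carries no linked term. Migraine history has its own CRF, and the documents do not show that a plain 'Migraine' entry exists under Medical History to link to. The sponsor clearly thought about preventives, since the string guard exists and the definition was revised in SAP Version 4. The medication listing flags acute and prophylactic migraine drugs, and SAP Section 7 lets conventions be refined in dataset specifications.

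Much of this stands: the number of affected subjects is unknown and could be zero. It does not remove the gap. Nothing in the SAP says the link is blank for preventives, and a preventive recorded under another indication and linked to a migraine term is still captured. A listing can reveal a misclassified drug but does not change the derivation. The latitude in Section 7 is stated for that section's conventions; the definitions at issue are in 6.2.6.3 and 9.2.1.1.

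**Conclusion.** The gap in the rule is real, but its effect is conditional. As written, a daily preventive linked to a bare 'Migraine' or 'headache' term makes every migraine day within its dates an acute medication day, contrary to the objective 12 estimand. Under the assumed 8 migraine days with 4 to 6 already counted, the mean rises by 0.2 to 1.6 days per month for shares of 10% to 40%. No share is supported by the documents. Severity is low: one exploratory endpoint, summarised descriptively.

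Two stronger readings are tempting. A reader might infer that every subject on a permitted preventive has all migraine days scored as acute. The text does not support that, because capture needs the link, a listed frequency and in-range dates.

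A reader might also size the effect against nonstudy acute drugs alone. With 3 such days out of 8, the mean (1 − s) × 3 + s × 8 goes from 3.0 to 3.5, 4.25 or 5.0 for s = 10%, 25% or 40%, that is +17%, +42% or +67%. That is not the endpoint's scale. OL rimegepant dates already count, and Protocol 5.5.2.2 makes rimegepant the first treatment for moderate or severe attacks in the OLE Phase, so fewer days are left to add.

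**What to change.** In SAP 6.2.6.3, add to the second bullet of the acute headache definition: 'and not a prophylactic migraine medication'. Section 9.2.1.1 needs no change, because it selects only from that class.

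Before the LSLV database lock, list the medications that enter the class only through a linked 'migraine' or 'headache' term and have one of the six daily frequencies. Review them by drug name and frequency and reclassify preventives. This covers preventives recorded under another indication, which the added clause misses. The listing should omit the double-blind arm, since the study is unblinded after the PCD lock (SAP 2.3).

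Do not use Protocol Appendix 2 as an automatic name filter. It is open-ended, closing with other locally recognised preventives, and it includes gabapentin, which exclusion criterion 6a lists as a non-narcotic analgesic. A filter could therefore miss preventives and drop genuine acute use.

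The cost is one clause and one short listing review, with no new data. Objective 12 is not among the PCD report outputs in SAP 8.1, so that report is unaffected.
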